Announcements will be posted in OSU employee newsletters, volunteer mailing lists, department mailing lists, and social media. Interested participants will be asked to email the study team. Study personnel will send a response email to determine if the participant is eligible to participate. Pre-screen questions will identify potential participants who meet the following criteria:

1. Age 18 or older
2. Be a care provider to a child who is up to 2 years of age
3. Have installed a child safety seat in the last 2 years
4. Able to lift and install a child safety seat into a vehicle
5. English-speaking

Participants who meet the above criteria will be asked to schedule an individual appointment.

Enrollment

Participants will be enrolled for one 30 minute time slot. Upon arrival at the scheduled time, participants will be briefed on the study protocol, sign the IRB approved consent form, incentive payment receipt, and will be given the incentive payment.

Session Protocol

Each participant will complete the consent process and sign the consent form. The participant will be asked to install the prototype car seat into a vehicle. A basic set of written instructions and labels on the car seat will be provided. The researcher will explain that they cannot answer any questions during the installation and that the participant may take as long as needed. If a participant completes the installation without using the load leg, this outcome will be noted and then the participant will be prompted to re-install the child seat using the load leg. When each installation is completed, the participant will be led away from the vehicle while a researcher evaluates their work. A researcher who is a CPST will use a data collection form to keep track of all installation errors committed by the participants. The primary outcomes of interest are the rate of load leg installation (without being prompted to use this feature) and correct installation of the load leg. Other errors of interest include routing of the seat belt or lower anchor straps, looseness of attachment, recline angle, etc. A handheld tension gauge will be used to quantify installation tightness. All other metrics are a visual pass/fail metric.

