Following the installations, participants will complete a short survey with open-ended queries to describe facilitators or barriers they experienced while installing the seat, as well as what they liked or did not like about the seat. They will use a Likert scale to rate their self-efficacy in installing the seats, if they believed they were installed correctly, and general ease-of-use. Socio-demographic data will also be collected (e.g. gender, age, and socioeconomic status). After study procedures are completed, the researcher will demonstrate how to correctly install the seat and provide the participant with educational materials.

Internal/external validity

Product usability studies are an effective, low-risk way to obtain information about a product design. Published work exists as a model for product usability protocols (for example: Mirman et al. 2015, Mansfield et al. 2018). Product usability studies help to highlight consumer habits and attitudes which engineers and product designers may not be aware of.

Data/statistical analysis

The percentage of participants who install with the load leg (without being prompted) will be recorded. Any installation errors associated with the load leg will also be recorded. Other errors will also be recorded as a percentage of the study sample (belt routing, looseness of attachment, etc.). The rates of these common errors will be compared to those reported in recent literature. There are currently no resources reporting typical error rates for load legs since this feature is not widely available in the current car seat market. The proposed study will provide a benchmark for this factor. Any installation errors with respect to the load leg will be analyzed for their likelihood of causing potential harm to the occupant.

The participant information collected in the surveys will be analyzed using descriptive and inferential statistics. Descriptive statistics such as means, standard deviations, medians, ranges, and frequency distributions will be calculated from the Likert scale data according to type of safety seat. Continuous data will be checked for normality. We will use either paired t-tests or Wilcoxon signed-rank test for correlated data to test the hypothesis of no change on ratings of ease-of-use and self-efficacy. Logistic regression will be used to predict correct load leg usage (pass/fail) using perceived self-efficacy, gender, and age of participants for each device.

Bibliography

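### The one survey described comes after any prompted re-installation and no split by prompted status is planned, so opinion ratings mix unaided and prompted experience, and the planned paired tests lack a described second rating

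*Combined protocol and SAP*

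**What the plan says.** Session Protocol describes one seat and one unaided attempt: "The participant will be asked to install the prototype car seat into a vehicle". If the participant finishes without the load leg, "this outcome will be noted and then the participant will be prompted to re-install the child seat using the load leg". Only these participants install twice.

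The survey follows: "Following the installations, participants will complete a short survey with open-ended queries to describe facilitators or barriers they experienced while installing the seat". On the ratings the protocol says: "They will use a Likert scale to rate their self-efficacy in installing the seats, if they believed they were installed correctly, and general ease-of-use". No rating is described between the first installation and the prompt, and no second survey is described.

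Data/statistical analysis says that descriptive statistics "will be calculated from the Likert scale data according to type of safety seat". It then plans "paired t-tests or Wilcoxon signed-rank test for correlated data to test the hypothesis of no change on ratings of ease-of-use and self-efficacy". It names no grouping of, or adjustment to, the rating summaries by whether the participant was prompted. The Objectives section makes opinions on the load leg design one of the two specific aims.

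**The concern.** The same form is completed under two conditions. An unprompted participant rates a single unaided installation. A prompted participant has been told to redo the job with the leg and has done so before rating anything. A summary over both groups depends on how many people were prompted as well as on how usable the seat is.

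The problem is sharpest for belief in correctness. For a prompted participant the item, as described, does not say which installation it means. If it means the first, the answer comes after the prompt has signalled that the leg was left out. If it means the second, it is not a rating of unaided use. Whether people who missed the leg thought they had finished correctly shows whether the labels and instructions fail unnoticed. The procedure as described does not capture that belief before the prompt.

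The paired tests add a second difficulty: they need two ratings per participant, and the procedure describes one rating occasion and one seat.

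**Working it through.** The documents state no figure on this point, so there is nothing to reproduce. The check is to set the procedure against the analysis, item by item.

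1. **Rating occasions.** Session Protocol describes one, after the last installation. The paired tests presuppose at least two for ease-of-use and self-efficacy. They do not cover belief in correctness, so for that item nothing in the text suggests a rating before the prompt.

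2. **Possible sources of a pair.** A pair could come from two seats or from two installations. Only one seat is described, and a second seat would not by itself supply a rating before the prompt. Two installations occur only among prompted participants, so unprompted participants cannot contribute a pair of that kind.

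3. **Grouping.** The only split named is by seat type. With one seat, that puts every participant in one group.

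4. **What can be recovered later.** Prompted status is noted for each participant, so ratings can be split at analysis. But a prompted participant's single rating equals the rating of the first, unaided installation plus the change caused by the prompt and second attempt: one observation, two unknowns. Comparing the groups does not separate the two parts, because people who missed the leg may have differed in confidence or ease-of-use before any prompt.

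5. **Scale of a possible shift (illustration only).** Let q be the share prompted and d the average change in a prompted participant's rating caused by the prompt and second attempt. If all ratings are averaged together,

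   reported mean = mean first-installation rating + q × d.

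   The documents give neither q nor d. Assuming q from 0.10 to 0.50 and d from 0.5 to 1.0 points in absolute size:

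| q | d = 0.5 | d = 1.0 |
|---|---|---|
| 0.10 | 0.10 × 0.5 = 0.05 | 0.10 × 1.0 = 0.10 |
| 0.50 | 0.50 × 0.5 = 0.25 | 0.50 × 1.0 = 0.50 |

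The shift runs from 0.05 to 0.50 points. Its sign is open: the prompt could lower confidence, or practice could raise ratings.

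**The case against.** The strongest reply has four parts.

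- **The timing has a reason.** The aim concerns opinions on the load leg. Someone who omitted it has not used it, and surveying after the prompted attempt ensures that each respondent has been asked to install with the leg before rating the seat. This stands. It rules out treating the first-installation rating as the sole main summary, but not collecting that rating as well.
- **The paired tests imply that two ratings were intended.** A reader might infer from the procedure that ratings are certainly taken only once and that the unaided rating is lost for all items. The documents do not support that for ease-of-use and self-efficacy, where procedure and analysis disagree. The reply does not reach belief in correctness. Nor does an intended second rating settle when it is taken or which installation it describes.
- **Pooling is not stated.** This also stands: mixing is inferred from the absence of a split. Reporting by prompted status needs no change to data collection.
- **The form is not in the documents.** Its wording may be clearer than the description, "They will use a Likert scale to rate their self-efficacy in installing the seats, if they believed they were installed correctly, and general ease-of-use" can be read as asking for overall ratings, and the open-ended questions let a prompted participant explain why the leg was missed. It is therefore too strong to say that the barrier answers describe only the prompted attempt. Clearer wording would still not put the belief rating before the prompt.

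A reader might also infer a known bias in the opinion results. The figures in the working rest on assumed inputs with an unknown sign and do not show one. A lower score among prompted participants would not show one either: if 80% of unprompted and 40% of prompted participants believed the seat was correctly installed, and half were prompted, the overall figure would be 0.5 × 80% + 0.5 × 40% = 60%. That could be the true unaided figure with no distortion at all.

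**Conclusion.** The point holds in a limited form. Followed as written, the plan combines ratings given under two conditions. It leaves the belief-in-correctness rating of prompted participants ambiguous and taken after the prompt. It also plans paired tests for which the procedure describes no second rating. The Session Protocol and Data/statistical analysis sections must be reconciled.

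Neither the size nor the direction of any shift can be determined from the documents. The conclusion assumes that the survey is given once, where the procedure places it, and that the summaries use no grouping beyond the one named.

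A reader might infer that the primary results are compromised. They are not: load leg outcomes recorded at the first installation are fixed before any survey is given. What is affected is the opinion aim, chiefly the missing rating before the prompt, which cannot be recovered once the session is over. The change is worth making, but this is not a fatal flaw.

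**What to change.** 1. **Analysis, no cost.** Report the Likert ratings separately for prompted and unprompted participants, using the prompt status already noted. This can be done even if data collection is unchanged.
2. **Session Protocol and survey form.** Have every participant answer the Likert items, at least belief in correctness and ease-of-use, right after the first completed installation and before any prompt. Prompted participants repeat them after re-installation. Each item names the installation it refers to. Include self-efficacy on both occasions if its paired test is kept. Wording that does not mention the load leg before the prompt would limit priming.
3. **Paired test.** Limit it to prompted participants' first and second ratings, and state that the number of pairs is the number prompted.
4. **Presentation.** Show first-installation and post-prompt ratings side by side. Do not make the first-installation rating the sole main summary, because participants who omitted the leg had not yet used it.

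The cost is new wording in the protocol and form, and one or two extra minutes for prompted participants. Unprompted leg use is already determined when the early items are given. The early items may slightly prime the second attempt, which should be kept in mind wherever correct leg installation is scored from that attempt.

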Official Title: Phase II - Safety-Enhancing Motor Vehicle Child Safety
Seat

NCT Number: NCT06384989

Document Date: May 2024

Document Contents: Study Protocol and Statistical Analysis Plan

Study Protocol and Statistical Analysis Plan

Background

Engineers from our Small Business partner, Minnesota HealthSolutions, have designed a new prototype child car safety seat. The car seat includes a load leg, which is a relatively new feature that braces the base of the car seat against the floor of the vehicle. The load leg helps to absorb crash forces and prevent movement of the car seat and its occupant during a crash. Load legs already exist on a few car seat models on the market today, but Minnesota Health Solutions has created a new design that absorbs energy in a novel way.

The research team from the Ohio State University (OSU) was involved in a Phase I SBIR with the prototype car seat. In that project, the prototype was shown to 15 volunteer participants (12 caregivers and 3 certified Child Passenger Safety Technicians (CPSTs)). The study participants practiced installing the car seat and gave verbal and written feedback on the understandability and ease-of-use of the load leg. They provided information about their families' travel habits and whether they saw value in the newly designed feature.

In this Phase II SBIR proposal, OSU will conduct additional human subjects testing to gauge the usability of the new car seat safety feature in a more in-depth and quantitative approach.

Objectives

The primary objective is to assess the usability of the load leg design for caregivers who must install the child safety seat into a vehicle. The specific aims are to quantify any errors committed by the participants while installing the car seat and to assess participants' opinions on the car seat's load leg design.

Research design

A descriptive study will be conducted to determine whether human subjects are able to install the new feature of the prototype car seat correctly. Participants will be presented with the prototype car seat and a set of basic written instructions and labels to guide their installations. The percentage of participants who use the new feature and use it correctly will be reported. Any installation errors on other parts of the child seat (seat belt, lower anchors, top tether) will also be reported.

Detailed study procedures

Recruitment

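### The three-predictor logistic model of correct load leg use has no safeguard against few failures or separation; a pre-specified Firth fit with profile intervals would supply one

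*Combined protocol and SAP*

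**What the plan says.** The last sentence of Data/statistical analysis begins "Logistic regression will be used to predict correct load leg usage (pass/fail") and continues "using perceived self-efficacy, gender, and age of participants for each device". The section gives no estimation method, predictor coding, or rule for sparse or separated data. Ordinary maximum likelihood is the natural reading.

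The surrounding text bears on this as follows:

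- **Sample size.** No Phase II number appears. The only head-count, in Background, belongs to Phase I: "In that project, the prototype was shown to 15 volunteer participants".
- **Outcome frequency.** No pass rate is assumed. The plan says "There are currently no resources reporting typical error rates for load legs".
- **Predictors.** Session Protocol says "They will use a Likert scale to rate their self-efficacy in installing the seats", without the number of scale points. Gender and age are collected, but no expected distribution is given.
- **Role.** Research design opens with "A descriptive study will be conducted to determine whether human subjects are able to install the new feature of the prototype car seat correctly". The primary outcomes in Session Protocol are unprompted use and correct installation of the load leg. They are reported as percentages and do not use the regression.

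**The concern.** A logistic model draws its information from the rarer of the two outcomes. If the load leg works as its designers hope, failures are the rarer outcome, so the better the design performs, the less this model can say. Few passes would thin it in the same way.

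Two things then go wrong with ordinary maximum likelihood. First, if everyone of one gender has the same result, or a combination of predictors splits passes from failures, some odds ratios have no finite estimate. Second, when the estimate is finite, it is biased in small samples.

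At stake are the reported predictors of correct use. Either they carry distorted odds ratios, or the fit fails and someone must drop gender, merge categories or change method after seeing the data.

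**Working it through.** **1. The plan's own figure.** There is none to reproduce: no N, pass rate, alpha, power or event count is stated. Everything below rests on assumed inputs.

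**2. Inputs.** From the plan: a binary outcome and three predictors, so at least three slopes and an intercept. Two assumed sets were simulated.

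- *Set A:* 30% men; odds ratio 2 per SD of self-efficacy (log odds ratio 0.69), 1.5 for gender (0.41), 1 for age.
- *Set B:* five-point self-efficacy item skewed to high scores, entered linearly; odds ratio 1.5 per point, 2.0 for gender, 1.0 per SD of age; 25% in the smaller gender group, with a 50/50 check; 800 studies per cell.

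**3. Information and non-estimability, set A.** Expected size of the rarer class = N × min(p, 1−p), where p is the pass rate; divide by 3 for events per predictor. For example, N=30 and p=0.8 give 30 × 0.2 = 6, and 6/3 = 2.

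| N | Pass rate | Rarer class | Per predictor | No finite ML estimate |
|---|---|---|---|---|
| 30 | 50% | 15 | 5.0 | 1.5% |
| 30 | 70% | 9 | 3.0 | 11% |
| 30 | 80% | 6 | 2.0 | 23% |
| 30 | 90% | 3 | 1.0 | 56% |
| 50 | 50% | 25 | 8.3 | 0.2% |
| 50 | 70% | 15 | 5.0 | 2% |
| 50 | 80% | 10 | 3.3 | 8% |
| 50 | 90% | 5 | 1.7 | 33% |
| 100 | 50% | 50 | 16.7 | 0% |
| 100 | 70% | 30 | 10.0 | 0% |
| 100 | 80% | 20 | 6.7 | 0.4% |
| 100 | 90% | 10 | 3.3 | 10% |

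The 70-90% rows use 1,000 studies each and the 50% rows 600. Across repeat runs the ranges for 70-90% pass were 10-59% (N=30), 1-33% (N=50) and 0-11% (N=100).

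**4. The same question, set B.** Share with no finite estimate at n=30 / 60 / 100:

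| Pass rate | 25% in smaller gender group | 50/50 split |
|---|---|---|
| 50% | 7 / 0.4 / 0% | 0.1 / 0 / 0% |
| 80% | 41 / 15 / 5% | 13 / 1 / 0.1% |
| 90% | 65 / 38 / 23% | 45 / 13 / 4% |

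The gender balance of the volunteers therefore matters as well as N.

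**5. Bias among finite fits.** In set A at 70-90% pass, the mean self-efficacy log odds ratio is too large by 31-53% at N=30, 18-38% at N=50 and 5-10% at N=100, over repeat runs. At N=30 and 50% pass the excess is still about 31%. Set B agrees in most cells but not all: at n=100 and 90% pass the mean is 0.97 times the truth.

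Gender behaves differently. In set A its mean is 0.34 times the truth at N=30, 80% pass, and −0.29 against a true 0.41 at N=30, 90% pass, because separated samples drop out. In set B with a 50/50 split it is 1.17 times the truth at n=30, 50% pass.

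**6. Firth's penalised fit.** In set A the mean self-efficacy log odds ratio is 0.61-0.73 at N=30, 0.68-0.71 at N=50 and 0.67-0.69 at N=100, against 0.69. Its root mean squared error is below that of maximum likelihood in all 16 cells examined (N from 30 to 200, pass rates 50-90%). In set B at n=30, 80% pass, it is 0.51 against 0.70. For gender the error is not lower in every cell: in set B at n=60, 80% pass, it is 0.86 against 0.81, where maximum likelihood is scored only on the samples it can fit.

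**7. What the penalised fit costs and leaves.**

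- *Predicted probabilities.* The intercept equation is Σ[yᵢ − πᵢ + hᵢ(½ − πᵢ)] = 0, with Σhᵢ = 4 parameters. Mean prediction minus observed rate is therefore roughly (4/N)(0.5 − p). At N=30, p=0.8 this is (4/30)(−0.3) = −4.0 points; at N=100 it is −1.2. Simulation (set B) gives −3.1 and −1.0, because leverage is concentrated where πᵢ is nearer 0.5. At N=30 and 70-90% pass the pull is 2-4 points.
- *Precision.* In set B at n=30, 80% pass, the median 95% interval for the gender odds ratio has an upper-to-lower ratio of about 125, and power for self-efficacy is 6%.
- *All-pass samples.* At p=0.9 and n=20 their probability is 0.9²⁰ = 12%, matching the simulated 12%. No fit can learn a predictor effect from them.

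**The case against.** The strongest reply is that no probability of failure can be attached to this model, because the documents state neither N nor a pass rate. A reader might infer from the Phase I head-count of 15, or from the one-to-one sessions, that the model will probably break down. The documents do not support that. Fifteen is not the Phase II number, Phase II is described as deeper and more quantitative, and individual sessions set no ceiling on enrolment. A pass rate near 50% is also plausible for an unfamiliar feature installed without help, and there fits seldom fail. This part stands: the problem is conditional.

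A reader might also infer that every odds ratio would be exaggerated. The gender results show otherwise. Nor is the penalised fit free: the plan's verb is to predict, and an uncorrected Firth fit biases mean predictions, which maximum likelihood with an intercept does not.

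Finally, the plan does not exclude penalised estimation, a non-finite fit would be visible to the analyst, and the primary percentages are untouched. These points limit the impact. They do not remove the gap, because a visible failure with no agreed response is what forces a choice after the data are seen. The missing N does not excuse the omission either: in the cases examined, the penalised fit helps most when the rarer class is small and differs little from maximum likelihood when it is large.

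**Conclusion.** The concern holds in conditional form. The plan commits to a three-predictor logistic model without a sparse-data or separation rule and without the figures needed to judge whether one will be needed. Under set A, ordinary maximum likelihood has no finite estimate in roughly 10-60% of studies at N=30, 1-33% at N=50 and 0-11% at N=100 for pass rates of 70-90%, and in at most about 2% at 50%. With a rarer gender group (set B, 25%) the rates are higher, including 7% at n=30 and 50% pass. Finite self-efficacy estimates are generally inflated; gender estimates can err either way.

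N, pass rate, effect sizes, scale coding and gender mix are all assumptions, so these figures show a range of outcomes and are not a forecast. The weakness is confined to a supporting analysis in a descriptive study. It is worth repairing because the repair is cheap.

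**What to change.** Replace the regression sentence with:

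> *Correct load leg usage (pass/fail) will be modelled by Firth penalised-likelihood logistic regression on self-efficacy, gender and age, with profile penalised-likelihood 95% confidence intervals, and with an intercept correction if predicted probabilities are reported; results are exploratory.*

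The authors should also explain the closing words of "using perceived self-efficacy, gender, and age of participants for each device". Research design and Session Protocol describe one prototype, yet the same analysis section also refers to summaries by seat type. Clarifying is safer than deleting. If participants were divided between devices, each model would have still fewer events.

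The cost is one sentence and standard software. The downsides are slight shrinkage and, if the intercept correction is left out, the pull in predicted probabilities shown above. The change does not substitute for stating N and the expected number of failures, and the report should say plainly that intervals may be very wide.
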